### 5.1 Background Information

#### 5.1.1 Indication

Actinic keratosis (AK) is an ultra-violet (UV) light-induced pre-cancerous lesion of the skin that represents the initial clinical manifestation of intra-epidermal abnormal keratinocyte

proliferation (Röwert-Huber, 2007; Fernandez Figueras, 2017). Given the demonstrated potential for progression to invasive squamous cell carcinoma (SCC), dermatologists encourage and actively pursue treatment, as recommended in current national and international guidelines (Hofbauer, 2014; Werner, 2015; de Berker, 2017; Leitlinienprogramm Onkologie, 2019).

Actinic keratosis presents as erythematous, scaly patches on the skin of sun-exposed areas and so particularly affecting the face, scalp, and extremities, either as a single lesion or multiple lesions and may present in as an entire field (“field cancerization”) with widespread actinic damage, such as in areas on the forehead or the back of the hand (Dodds, 2014; Figueras Nart, 2018). Actinic keratosis is common in older, fair-skinned populations of European ancestry, and is more frequently observed in men (Flohil, 2013).

Precise estimates of AK prevalence are difficult, owing to its strong association with increased age. The prevalence of AK in the US has been reported to range from 11% to 26% (Salasche, 2000). Recent studies in Europe suggest that AK prevalence there ranges from 33% to 49% for men and 14% to 28% for women (Eder, 2014, Tizek, 2019, Flohil, 2013, Ferrández, 2016, Farnoli, 2017, Dziunycz, 2018).

In some cases, AK represents a carcinoma *in situ* of the skin, and when left untreated, AK can progress to invasive SCC (Röwert-Huber, 2007; Werner, 2013; Fernandez Figueras, 2017). Cutaneous SCC represents 20% to 50% of skin cancers (Que, 2018) and poses a significant threat due to its ability to metastasize to any organ in the body (Burton, 2016). Up to 65% of SCCs arise from pre-existing AK; however, the risk of progression to SCC of a single AK lesion per year has been reported to be very low, 0% to 0.075% in patients without a previous history of non-melanoma skin cancer (Marks, 1988), and up 0.53% per lesion in patients with a prior history of non-melanoma skin cancer (Werner, 2013; Green, 2017).

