### 8.2 Inclusion Criteria

All of the following criteria must be met for inclusion of a patient in the trial:

1. Male or female and  $\geq 18$  years old at the time of consent
2. Having a TF on the face or balding scalp (excluding lips, eyelids, and inside nostrils and ears) that
  - measures approximately 100 cm^2 (eg, mid face) and
  - contains 4 to 12 clinically typical, visible, and discrete AK lesions within the TF
3. If a woman of childbearing potential (WOCBP), ie, fertile, defined as a female in the life period from menarche and until becoming post-menopausal (no menses for 12 months without an alternative medical cause) or permanently sterile (with hysterectomy, bilateral salpingectomy, or bilateral oophorectomy at least 3 months prior to Screening), she must:
  - have a negative urine pregnancy test using a highly sensitive method at screening and on Day 1 prior to treatment administration
  - be using highly effective methods of birth control (defined in [Appendix 1](#)) for at least 30 days or 1 menstrual cycle, whichever is longer, prior to the study treatment and must agree to continue use during the study period and until at least 30 days or 1 menstrual period, whichever is longer, after the last dose of investigational product
  - agree to have pregnancy tests while in the study and at the end of the study (according to the Schedule of Assessments in Table 1)
4. Sexually active males with partners who are WOCBP must agree to use two forms of contraception, one of which must be barrier contraception, from Screening through 90 days after their last dose of study treatment. All male patients must agree not to donate sperm or attempt conception from Screening through 90 days following their last dose of study treatment.
5. Willing to avoid excessive sunlight or UV light exposure, including the use of tanning beds, to the face or scalp during the study
6. Ability to understand the purpose and risks of the trial, willingness and ability to comply with the protocol, and provided written informed consent in accordance with institutional and regulatory guidelines

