Weight of study drug packets ^f		X			X				
Standardized photography of the treatment field	X	X ^{a,l}			X	X	X	X	X
AEs ^g	X	X	X		X	X	X	X	X ^h

M-14867-32

Statistical Analysis Plan Status: Version (17 Jan 2023)

Period	Screening*	Treatment		Response Assessment					
		1	2	At home, once-daily self-administration ^m	3	4	5	6	7
Visit(s)									ET/EoS
Day(s)	-28 to -1		1 (Baseline)	2 to 5	5	8	15	29	57
Visit Time Window (days)	None	None			None	±2	±2	±3	±3
Treatment Field location		X ^a		X	X	X	X	X	X
Focused dermatological exam of treatment field									
Local tolerability		X ^a			X	X	X	X	X ^b
Hypo- and hyperpigmentation and scarring		X ^a			X	X	X	X	X ^b
AK Lesion count in the TF	X	X			X	X	X	X	X

Abbreviations: AE=adverse event; AK=actinic keratosis; ECG=electrocardiogram; ET=Early Termination; EoS=End of Study; ICF=informed consent form; TF=treatment field; WOCBP=women of child-bearing potential.

* Patients who require a washout period from prohibited concomitant treatments should be seen and sign the ICF prior to the Screening visit, to ensure the necessary washout before starting treatment. No trial assessments will be performed on that date and the Screening visit will be scheduled according to the washout length required for the specific medication stopped.

^a Assessments/procedures performed before treatment administration. Day 1 evaluation will serve as a Baseline for these assessments.

^b Patients must be in a supine position for 5 minutes prior to ECG.

^c Highly sensitive urinary pregnancy test performed at the clinical trial site.

^d Physical examination to include height, weight, and an assessment of head, eyes, ears, nose and throat, integumentary/dermatological, gastrointestinal, cardiovascular, respiratory, musculoskeletal, neurological systems, and an expanded dermatological examination to cover the sun-exposed areas, where photo-damage is likely. Height is measured only at screening.

M-14867-32

Statistical Analysis Plan Status: Version (17 Jan 2023)

^e On Day 5 patients are to bring all 5 study drug packets back to the site (used and unused) with their respective torn parts in the individual closed zipper storage bag provided in the study kit.

^f All study drug packets will be weighed together in their respective closed zipper storage bag before and after use (including the torn opening part).

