14.1 Local Tolerability Assessment

Local tolerability is assessed based on the review of the following signs in the treatment field: erythema, flaking/scaling, crusting, swelling, vesiculation/pustulation, and erosion/ulceration and will be evaluated both individually and as a composite score (total of the 6 individual scores ranging from 0 to 18). These signs will be graded as: 0=absent, 1=mild (slightly, barely perceptible), 2=moderate (distinct presence), and 3=severe (marked, intense). If one or more individual score is missing, the composite score will be set as missing.

The maximum local tolerability signs composite score across visits will be derived as the maximum local tolerability assessment (LTA) composite score observed post-baseline for a patient. The maximum local tolerability of individual signs across visits will be derived as the maximum LTA of an individual sign observed postbaseline for a patient.

Descriptive statistics will be presented for local tolerability signs composite score by visit, and for maximum local tolerability signs composite score across post-baseline visits. Frequency and percentages by visit of patients presenting any individual and composite local tolerability signs and associated CI based on exact Clopper-Pearson method will be presented. The presence of any individual and composite local tolerability sign is defined by a score of >0. Frequency and percentages by visit for specific local tolerability individual signs results and maximum local tolerability of individual signs across post-baseline visits will also be provided.

The 95% CI will be presented for the median of the maximum local tolerability composite score.

Figures presenting the number of patients with each local tolerability individual sign (absent/mild/moderate/severe) by visit, and a figure presenting the mean local tolerability composite score by visit will be produced.

The time to maximum LTA score for each individual sign and the time to maximum LTA composite score will be calculated as the time (in days) from the first dose of study treatment to the time of the first occurrence of the maximum LTA score observed post-baseline for each individual sign and composite score, respectively. That is, for each individual sign, time to maximum LTA, in days, will be calculated as follows:

(Date of first post-baseline occurrence of maximum LTA score for an individual sign – Date of first dose)

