Time to maximum composite LTA, in days, will be calculated as follows:

(Date of first post-baseline occurrence of maximum composite LTA score – Date of first dose)

If a patient's maximum composite/individual sign LTA score stays at 0 throughout the study, the patient will be considered censored at his last LTA score observation. The time to maximum composite/individual sign LTA will be analyzed using Kaplan Meier estimation, overall and by strata as applicable. The Kaplan Meier estimates will include the 25th, 50th (median), and 75th percentiles along with their 95% CIs. The standard errors (SE) will be computed using the Greenwood's formula. The CI for the median will be calculated as per Brookmeyer and Crowley and the CIs for the 25th and 75th percentiles will be calculated using the log-log transformation.

Survival curves will also be presented and all local tolerability assessments will be listed.

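### SAP 14.1 does not separate pre-existing local signs from new or worsened ones, because no planned summary compares a patient with their own Day 1 score

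*SAP*

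**What the plan says.** SAP 14.1 grades six signs from 0 to 3, sums them to a composite of 0 to 18, and plans three kinds of summary.

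- **Presence.** The planned table is "Frequency and percentages by visit of patients presenting any individual and composite local tolerability signs", with exact confidence intervals, and "The presence of any individual and composite local tolerability sign is defined by a score of >0".
- **Maximum.** The maximum for an individual sign "will be derived as the maximum LTA of an individual sign observed postbaseline for a patient". The composite maximum is built in the same way.
- **Time to maximum.** This runs from first dose to the first occurrence of the maximum and is analysed by Kaplan-Meier. The only censoring rule covers scores that never leave zero: "maximum composite/individual sign LTA score stays at 0 throughout the study, the patient will be considered censored at his last LTA score observation".

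The schedule in SAP 3.2 (Table 1) places a local tolerability assessment before dosing on Day 1, and its footnote a says "Day 1 evaluation will serve as a Baseline for these assessments". Section 14.1 does not use that score in any within-patient comparison. It closes with "Survival curves will also be presented and all local tolerability assessments will be listed", and SAP 15.2 plans nothing further.

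Elsewhere the SAP does use baseline. Section 7.2 gives a general change-from-baseline formula. Change from baseline or shift tables are planned for lesion counts (13.1), scarring and pigmentation (14.2), laboratory values (14.4), vital signs (14.5) and ECG (14.6).

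**The concern.** Two of the six graded signs are also features of the disease. Protocol 5.1.1 states: "Actinic keratosis presents as erythematous, scaly patches on the skin of sun-exposed areas". Under Protocol 8.2 every eligible field "contains 4 to 12 clinically typical, visible, and discrete AK lesions within the TF". The threshold for grade 1 is low, a sign that can only just be seen, so non-zero Day 1 scores for erythema and flaking/scaling are plausible.

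The protocol itself allows for them. In 10.5.2.1, follow-up of a local sign after Day 57 may end on resolution, on return to the baseline value, or on stabilisation. Listing the first two separately makes sense only if a baseline value can be above zero. The Phase 2 summary in 7.2.3, where signs are said to have gone back essentially to baseline levels by Day 29, is consistent with this but does not prove it.

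Tolerability is part of the primary objective and there is no control arm, so Day 1 is the only within-patient reference. A patient who is back at a Day 1 erythema of 1 may stop follow-up under the protocol, yet the Day 57 table still counts that patient as having a sign. No planned table says how many such patients there are.

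**Working it through.** **The plan's own figure.** No Day 1 prevalence is stated, so nothing on this exact point can be reproduced. The related figure is the sample-size assumption in SAP 5: 90% with any sign, n = 100, interval width about 11 points. The Wald width is 2 × 1.96 × √(0.90 × 0.10 / 100) = 11.76 points, which is consistent. The exact interval for 90/100 is 82.4% to 95.1%, 12.7 points wide. Neither figure supports or refutes the concern. The 90% serves only as an input below.

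**Bound on the share who worsened.** Let R be the percentage with a score above 0 after baseline and b the percentage with a score above 0 on Day 1.

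- Every patient with a sign after baseline and none on Day 1 has worsened, so worsened ≥ max(0, R − b).
- Worsening requires a post-baseline score above 0, so worsened ≤ R.

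The table takes R = 90 from SAP 5. All values of b are assumed. The last column is a middle case in which Day 1 signs persist and worsening is independent of them. It solves 1 − (1 − b)(1 − w) = 0.90 for w, with b and w as proportions.

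| b assumed | Lower bound, R − b | Upper bound, R | w in the middle case |
|---|---|---|---|
| 0% | 90% | 90% | 90.0% |
| 10% | 80% | 90% | 88.9% |
| 25% | 65% | 90% | 86.7% |
| 50% | 40% | 90% | 80.0% |
| 75% | 15% | 90% | 60.0% |
| 90% | 0% | 90% | 0.0% |

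At b = 20% the range is 90 − 20 = 70% to 90%. For a late visit with R = 20% and b = 20% (both assumed) it is 0% to 20%.

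**Why by-visit tables cannot close the range.** Take n = 100, one sign, Day 1 against Day 57. Case B is a logical illustration, not an expected result.

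- Case A: 20 patients score 1 at both visits and 80 score 0 at both.
- Case B: 20 go from 1 to 0, 20 others go from 0 to 1, and 60 score 0 at both.

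Both cases show 20/100 = 20.0% (exact 95% interval 12.7 to 29.2) at each visit, the same grade table and the same mean of 0.20. The share worse than Day 1 is 0/100 = 0.0% (0.0 to 3.6) in A and 20/100 = 20.0% (12.7 to 29.2) in B.

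**Time to maximum.** The formula is date of first maximum minus date of first dose, here with scheduled visits on Days 5, 8, 15, 29 and 57.

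| Day 1 score | Later scores | Result under 14.1 |
|---|---|---|
| 1 | 1, 1, 1, 1, 1 | event at 5 − 1 = 4 days |
| 2 | 1, 1, 1, 1, 1 | event at 4 days |
| 2 | 1, 2, 1, 1, 1 | event at 8 − 1 = 7 days |
| 0 | 0, 0, 0, 0, 0 | censored |

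The first three patients never exceed their Day 1 score, yet all three enter the Kaplan-Meier percentiles as events.

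**The case against.** The strongest reply is that the planned output already shows whether the problem exists. SAP 7.3 (Table 2) makes Baseline an analysis visit for local tolerability. Section 14.1 uses by-visit wording for presence, grades and composite, and limits only the maxima to post-baseline visits. Day 1 prevalence should therefore be printed beside the later visits. If it is near zero, the concern disappears. With complete data, mean change in the composite equals the difference between means already planned. All assessments are listed, for about 100 patients. This stands at group level. It does not give a within-patient count, and tallying one from a listing is not a planned analysis.

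Eligibility also limits Day 1 scores. Protocol 8.3 excludes hyperkeratotic or hypertrophic lesions, other skin disease that makes the field hard to examine, and interfering eczema, psoriasis or seborrheic dermatitis. This lowers the likely prevalence but does not make it zero.

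Some consequences are already referenced to baseline. A sign that interrupts treatment or needs medication is reported as an AE, and a treatment-emergent AE must be new or increased in severity. These rules cover the signs with clinical consequences but do not tabulate change in the scores.

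A reader might also infer more than the documents support:

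- *That the SAP attributes every score above 0 to treatment.* It does not. Section 14.1 tabulates patients presenting a sign and makes no causal claim, so attribution would be the reader's step.
- *That worsening is hidden.* A change from 1 to 3 still appears as severe.
- *That the SAP departs from the protocol.* Section 14.1 follows the endpoints in Protocol 6.2.1, so the request is an addition.
- *That the signs of particular interest are inflated.* Nothing in the documents links vesiculation/pustulation or erosion/ulceration to untreated AK.

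**Conclusion.** The concern holds as a gap in the planned summaries. Presence, maximum and time to maximum all ignore the patient's own Day 1 score, so signs present before treatment are not separated from new or worsened ones. The direction is possible overstatement of mild signs, in erythema, flaking/scaling, the any-sign rate and the composite.

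The size cannot be stated. It depends on Day 1 prevalence, which the documents do not give. The bounds above are logical limits on assumed inputs and do not estimate a bias. A reading that the headline rates are materially wrong is not supported, because Day 1 prevalence may prove small and the by-visit tables should show it.

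The addition is still worth making. It is cheap, it follows the method of the neighbouring section 14.2, and it gives a single-arm trial a within-patient answer that the by-visit tables cannot.

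**What to change.** Keep all planned summaries. Add to SAP 14.1, for patients with a baseline and a post-baseline result (the paired-data principle already used in 14.2):

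1. The number and percentage of patients whose maximum post-baseline score exceeds their Day 1 score, with Clopper-Pearson 95% intervals. Report this for each sign and for any sign, meaning at least one sign above its own Day 1 score.
2. One shift table per sign from Day 1 score to post-baseline maximum, 0–3 by 0–3.

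By-visit shift tables and composite change from baseline are optional. Shifts for every visit would mean 6 signs × (5 visits + 1 maximum) = 36 panels, or 36 × 3 = 108 with overall, face and scalp, which is more than the question needs.

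The cost is SAP wording, six shift tables and one rate table (7 × 3 = 21 tables if shown overall and split by face and scalp). No new assessment and no protocol amendment are needed. The change should be recorded in SAP Section 16.

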14.2 Scarring, Hypopigmentation and Hyperpigmentation

The number and percentage of patients with absence or presence of scarring, hypopigmentation, and hyperpigmentation in the TF and associated 95% CIs will be presented separately at scheduled visits.

Shift tables representing the change from baseline in scarring, hypopigmentation, and hyperpigmentation in the TF will be provided separately as well. Only patients with a baseline result and a result at the specified post-baseline visit for the parameter will be considered in the shift tables.

Scarring, hypopigmentation and hyperpigmentation evaluations will be presented in a listing.

14.3 Adverse Events

AEs will be coded according to the MedDRA, Version 25.0.

TEAEs will be defined as any AEs with onset date/time on or after the first study treatment dosing and prior to the last date of study treatment dosing + 57 days (inclusive), or as any AE that was present prior to the first dose of trial drug but increased in severity on or after the first study treatment dosing and prior to the last date of study treatment dosing + 57 days (inclusive). AEs starting on the first study treatment dosing date and related to a pre-dose study assessment will not be considered as TEAE. See Appendix 2 for handling of completely or partially missing dates and time for AEs. In the case where it is not possible to define an AE as treatment emergent or not, the AE will be classified as treatment emergent.

Overall summaries of AEs will be presented by number and percentages of patients with and number of events of AEs, TEAEs, study treatment-related TEAEs, TESAEs, TEAEs by worst severity, TEAEs leading to study treatment discontinuation, TEAEs leading to study discontinuation, application site TEAEs, AESIs, and TEAEs with an outcome of death.

Frequency and percentage of patients who experience TEAE will be summarized by SOC and PT within SOC. Unless otherwise specified, a patient experiencing the same TEAE multiple times will be counted only once for the corresponding PT. Similarly, if a patient experiences multiple TEAEs within the same SOC, the patient will be counted only once for that SOC. TEAEs will be sorted alphabetically by SOC and within each SOC the PT will be presented by decreasing order. Treatment-emergent SAEs, TEAEs leading to study treatment discontinuation, TEAEs with an outcome of death and TEAEs leading to study discontinuation will be summarized similarly.

Frequency and percentage of patients who experience TEAE will also be summarized by SOC, PT and worst severity (mild/moderate/severe). TEAE with an unknown severity will be considered as severe. If a patient experiences more than one TEAE within different severity categories within the same SOC/PT, the patient will be counted only once under each SOC/PT under the worst severity.

Frequency and percentage of patients who experience study treatment-related TEAE will be summarized by SOC and PT. A study treatment-related TEAE is defined as any TEAE that is assessed by the Investigator as possibly related or related to study treatment. A not study treatment-related TEAE is defined as any TEAE that is assessed by the Investigator as unlikely or not related to study treatment. TEAE with an unknown relationship will be considered as treatment-related.

Frequency and percentage of patients who experience application site TEAE will be summarized by PT. AESIs will be summarized similarly.

Frequency and percentage of patients who experience TEAE in the application site pain preferred term will be summarized by PT and lowest level term (LLT). Unless otherwise specified, a patient experiencing the same TEAE multiple times will be counted only once for the corresponding PT/LLT.

All AEs will be listed. Separate listings will also be provided for AEs leading to death, all SAEs, all TEAEs leading to study discontinuation, and all AESIs.

14.4 Clinical Laboratory Parameters

Laboratory parameters of hematology, blood chemistry, and urinalysis will be summarized using descriptive statistics at baseline and at subsequent visits. Change from baseline values will be presented for each post-baseline assessment. Frequencies and percentages for each result will be provided for qualitative urinalysis data.

In addition, shift tables (for hematology, blood chemistry, and quantitative urinalysis: low-normal-high at baseline versus low-normal-high at follow-up in a 3-by-3 contingency table; for qualitative urinalysis: normal-abnormal at baseline versus normal-abnormal at follow-up in a 2-by-2 contingency table) will be provided to assess changes in laboratory values from baseline. Only patients with a baseline result and a result at the specified post-baseline visit for the parameter will be considered in the shift tables.

Separate listings of all data for hematology, blood chemistry, and urinalysis will be provided. In addition, separate listings of data for hematology, blood chemistry, and urinalysis will be provided for each parameter where a patient had at least one clinically significant or not clinically significant abnormal result.

A listing will be provided for Pregnancy test results.

